	
the imaging schedule may be modified based on the imaging data from the first cohort of patients.
 
The optimal time point for PET scanning will be determined based on the analysis of the tumor to background ratio and tumor to blood pool ratio at different timepoints. Tumor to background ratio is defined as the ratio between tumor tracer uptake and the radioactivity on the opposite site or gluteus maximus, etc. The first PET scan will be performed in combination with a low-dose CT scan for attenuation correction and anatomic reference. An independent radiology review committee (IRC), consisting of principal investigator and nuclear medicine physicians, will be established to evaluate all imaging data.
 
If there is no radioactivity or a small amount of radioactivity in the target lesion as evaluated by the IRC, and the safety criteria are met, the dose will be escalated per the escalation guidelines. If the tumor to background ratio is high per the IRC, three patients will be enrolled at the next higher level and the IRC will determine whether dose escalation should stop based on the imaging data from these three patients. Blood samples will be collected from a peripheral vein to evaluate ADA, PK and the radioactivity in the circulation.
 
 • The time points for blood sample collection are as follows: within 30 minutes before injection of SNA002, at 2 ± 1 minutes, 5 ± 1 minutes, 10 ± 1 minutes, 30 ± 2 minutes, 50 ± 5 minutes, 100 ± 5 minutes and 150 ± 10 minutes post injection. All blood samples are sent to the central laboratory for PK analysis. Radioactivity in the blood sample (whole blood and serum) will be obtained using a γ-well-type detector and measured activity concentrations will be converted to percentage injected activity/L. • Urine sample will be collected to evaluate the renal excretion of radioactivity before injection, at 90 ± 30 minutes, 180 ± 30 minutes and 300 ± 30 minutes post injection. Counts in aliquots of serum or urine will be obtained using a γ-well-type detector and measured activity concentrations will be converted to percentage injected activity/L. 
Blood samples will be taken 30 minutes before administration, on $D6\pm 1$d and $D28\pm 2$d, and will be sent to the central laboratory for ADA analysis. Patients were discharged from the study after blood samples were collected on $D28\pm 2$d. Following the last PET scan, tumor biopsies or operation (if surgery is available) will be obtained. The investigator will determine the number and location of lesions for biopsy for each patient in consultation with the surgeon or interventional radiologist; these should be easily accessible and have positive or negative tracer uptake. Biopsy sites should not exceed 5 for each patient and ideally include both negative lesions and positive lesions. If taken an operation on tumor, the IRC will observe IHC result of tumor and PET scan.
 
The study will be end for patient after completing blood collection on $D28\pm 2$d.
 
Region-of-Interest Definition
 
Regions of interest (ROIs) will be used to determined SNA002 uptake in different organs. Organs with tracer uptake will be drawn using PMOD software based on the PET image, including all activities on the PET images that are contributing to the organ. For organs without tracer uptake, organ delineation will be based on CT data.
 
To calculate the biodistribution and dosimetry in normal organs with tracer uptake, a semiautomatic (region grow) method will be used to delineate the ROI on the PET images. For normal organs without tracer uptake, the ROI will be delineated based on CT scan.
 
Dosimetry
 
Time-activity curves were derived from volumes of interest for each source organ (i.e., brain, heart, lungs, liver, spleen, kidneys, and thyroid) delineated on the whole-body images using PMOD.
 
To define volumes of interest (VOIs) the dynamic study was loaded with all or some frames averaged, depending on the evaluated organ. VOIs were defined manually for heart, liver, gallbladder, kidneys with all frames averaged.
 
Using the PMOD software the VOIs consisted of regions of interest (ROIs) which were defined at the outer contour of the organ. In this way (decay-corrected) TACs of the organs' average radioactivity concentrations and their volumes were obtained.
 
An example, FYI: Source Organs: For dosimetric calculations, the following source organs were included: kidneys, red marrow, cortical bone mineral surface, trabecular bone mineral surface, urinary bladder content, and remainder body. Red marrow activity uptake was estimated from venous blood sampling.
				

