8) Develop a plan for obtaining target lesion specimens (if applicable): Determine whether to collect tissue specimens after administration based on specific circumstances. If the subject has obtained a biopsy specimen within 2 weeks prior to enrollment and has obtained/can undergo immunohistochemical PD-L1 detection results (such as PD-L1 immunohistochemical detection of pathological tissues in different directions of the lesion collected through bronchoscopy within 2 weeks prior to enrollment), and no treatment has been given, no further biopsy is required. Otherwise, pathological specimens need to be collected in this clinical study. The collection method can accept biopsy or surgical resection of specimens, which is determined by the investigators based on the subject's situation.
 (note: the investigators can arrange for the subjects to enter a safe follow-up period after the subjects complete the tissue specimen collection (D2) or surgical specimen collection (D2-D5) during the trial period, or after the subjects who do not need to collect tissue specimens again complete all operations in D1, in order to shorten the waiting time for subsequent treatment from an ethical perspective).

9) Vital signs: Vital signs are evaluated at 6 ± 1 h after administration on D1.

10) Examination of injection site: observe injection site for redness, swelling, heat, pain, itching and other symptoms 6 ± 1 h after administration.

11) Record concomitant medications.

12) Record AEs.

D2 to D5

- 1) Target lesion specimen acquisition: Biopsy specimens can include endoscopic (such as gastroscopy, fiberoptic bronchoscopy, laparoscopy, etc.) and puncture biopsy specimens, which are generally conducted in D2. The preferred specimen for collection is the primary tumor lesion or metastatic lesion with the highest SUVmax; The collection principle is to collect at least one biopsy sample from the target tumor lesions that can be collected, and the maximum number of samples for the same patient is 5. Ideally, biopsies should be performed on both positive and negative lesions of the same patient under PET imaging. The location of specimen collection and the selected collection method will be determined by the investigators based on previous imaging results and the PET results of this experiment. Perform PD-L1 immunohistochemical detection after obtaining target tissue samples.

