9. ADA: blood samples were collected within 30 minutes before administration, on D6 ± 1d and D28 ± 2d during the safe follow-up period. All blood samples were tested in an independent third-party central laboratory.
10. Systemic PET-CT: Three systemic PET CT scans are performed at 15±5 minutes, 60±10 minutes, and 120±20 minutes after administration. Panoramic PET-CT scans performed after dosing were acceptable for 1 to 2 subjects in a dose group or each dose group and were required to cover at least one of these time points.
11. Measurement of Radiation Dose: measure the surrounding radiation dose at 4 ± 0.5 hours after administration.
12. PD-L1 Immunohistochemical Examination and Formulate a Plan for Obtaining Target Lesion Specimens (If Performed) : Obtain the PD-L1 immunohistochemical results of the subjects at the study site during the screening period. This experiment determines whether to collect tissue specimens after administration based

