on specific circumstances. If the subject has obtained a biopsy specimen within 2 weeks before enrollment and has not undergone any treatment, there is no need to perform another biopsy, otherwise the specimen needs to be collected again. Researchers need to determine the method of specimen collection based on the subject's situation, and can accept surgical resection of tumor tissue or biopsy for sampling. Surgical resection can be performed after 1 day of drug administration (i.e. after D2, surgical resection is generally performed between D2 and D5). Immunotherapy, chemotherapy, or radiation therapy should not be performed on the primary tumor disease during the period from drug administration to surgery. Biopsy sampling can include endoscopic (such as gastroscopy, fiberoptic bronchoscopy, laparoscopy, etc.) sampling and puncture biopsy sampling, generally conducted in D2. The preferred specimen for collection is the primary tumor tissue or metastatic lesion with the highest SUVmax. The collection principle is to collect at least one biopsy sample from the target tumor lesions that can be collected, and the maximum number of samples for the same patient should not exceed 5. Ideally, biopsies should be performed separately for positive and negative lesions under PET imaging in the same patient. The location of specimen collection and the selected collection method are determined by the researcher based on previous imaging results and PET results of this experiment. After obtaining target tissue samples, PD-L1 immunohistochemistry was performed at the research center.

13. Collection of Tissue Samples from Target Lesions (If Performed) :Specimens collected according to established target lesion specimen acquisition protocol from D2 to D5.
14. Examination of Injection Site: observe injection site for redness, swelling, heat, pain, itching and other symptoms 6 ± 1 h and 24 ± 6 h after administration.

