10.4.3 Analysis of the Secondary Endpoints

Immunogenicity evaluation

- Anti-SNA002 antibody: ADA blood samples are collected before administration and on D6 \pm 1d and D28 \pm 2d after administration for the detection of anti-SNA002 antibody in the independent third-party central laboratory.

Evaluation of correlation of expression between imaging and IHC

- The IHC analysis is conducted to the collected tumor tissue samples (tested by the independent third party central laboratory) and the results are compared with those of imaging. Take the immunohistochemistry result as the true values (if only baseline immunohistochemistry result is available, the baseline result is the true value; if both baseline and post administration immunohistochemistry results are available, then post administration results are true values) .Sensitivity [true positive/(true positive + false negative)], specificity [true negative/(true negative + false positive)], positive predictive value [true positive/(true positive + false positive)], and negative predictive value [true negative/(true negative + false negative)] are calculated. Explore the correlation between PET imaging features (such as tumor SUVs, tumor/muscle SUVs) and immunohistochemical results.

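### Sensitivity and specificity combine PET-selected biopsies with pre-PET tissue in one calculation, so they depend on which lesions were sampled; size and direction of any bias are unknown

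*Combined protocol and SAP*

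**What the plan says.** Section 10.4.3 takes IHC as the true value. Post-administration tissue takes precedence when both results exist; otherwise "if only baseline immunohistochemistry result is available, the baseline result is the true value". Sensitivity, specificity, PPV and NPV are then computed as simple 2x2 ratios: "Sensitivity [true positive/(true positive + false negative)], specificity [true negative/(true negative + false positive", and likewise for PPV and NPV. Nothing splits or weights the two tissue sources, and the section does not say whether the unit is the patient or the lesion.

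Pre-PET tissue enters because section 7.3.3 (D1, item 8) waives a new biopsy for a patient with a specimen from the two weeks before enrollment: "and no treatment has been given, no further biopsy is required".

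Post-PET tissue is chosen with the scan in view. In section 7.3.3 (D2 to D5, item 1), "The preferred specimen for collection is the primary tumor lesion or metastatic lesion with the highest SUVmax", and the site and method are "determined by the investigators based on previous imaging results and the PET results of this experiment". Sampling both kinds of lesion is a wish, not a rule: "Ideally, biopsies should be performed separately for positive and negative lesions under PET imaging in the same patient" (Table 4, footnote 12). The Protocol Summary adds, on biopsy sites, that "these should be easily accessible and have positive or negative tracer uptake". Each patient gives one to five samples.

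On reading order, footnote 12 also says: "Obtain the PD-L1 immunohistochemical results of the subjects at the study site during the screening period". The Protocol Summary has the IRC evaluate all imaging and also review the IHC results. Sections 7.3.3 (D2 to D5, item 5) and 10.4.3 send post-dose IHC to an independent third-party laboratory, while footnote 12 places it at the research center.

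**The concern.** When the test under study helps to decide which lesions receive the reference standard, the 2x2 table no longer mirrors the lesions present. Over-sampling PET-positive lesions inflates sensitivity and deflates specificity; taking one lesion of each kind can do the opposite. Mixing in tissue chosen without the PET changes the result again, by an amount set by the mix. A reader of the final figures could not separate how well the tracer performs from how the biopsies were chosen.

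A second, smaller issue concerns independence of the readings. For post-dose tissue, a PET impression exists before the IHC. Screening IHC, however, can be known before the scan and is the truth when it is the only result. The IRC handles both, and nothing requires its PET call to be fixed first. No size is claimed for this.

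**Working it through.** **The plan's own figure.** Four dose groups of 3 to 7 give 4 × 3 = 12 and 4 × 7 = 28 subjects, matching section 10.5. These are subject counts. No lesion count, accuracy target or sampling fraction is stated.

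**Assumed inputs (none from the documents).** True sensitivity Se = 0.70, true specificity Sp = 0.80, IHC-positive share p = 0.5. Let r be the biopsy rate of PET-positive over PET-negative lesions, and f the share of verified lesions from pre-PET tissue.

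**Formulas.** Among PET-selected lesions the cells are proportional to TP = r·p·Se, FN = p(1−Se), TN = (1−p)·Sp, FP = r(1−p)(1−Sp). Scale them to sum to 1, then mix with the r = 1 cells in proportion (1−f):f.

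**All tissue PET-selected (f = 0).**
- r = 2: TP 0.70, FN 0.15, TN 0.40, FP 0.20. Sensitivity 0.70/0.85 = 82%; specificity 0.40/0.60 = 67%.
- r = 4: sensitivity 1.40/1.55 = 90%; specificity 0.40/0.80 = 50%.

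**Half pre-PET tissue (f = 0.5).**
- r = 2: the scaled cells 0.483, 0.103, 0.276, 0.138 are averaged with 0.35, 0.15, 0.40, 0.10, giving 0.416, 0.127, 0.338, 0.119. Sensitivity 77%; specificity 74%.
- r = 4: 82% and 68%.

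**One PET-positive and one PET-negative lesion per patient.** Sensitivity = PPV/(PPV + 1 − NPV); specificity = NPV/(NPV + 1 − PPV).
- p = 0.5: PPV = 0.35/0.45 = 0.778 and NPV = 0.40/0.55 = 0.727, giving 74%/77%.
- p = 0.7: 66%/83%.
- p = 0.9: 56%/88%.

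So the direction depends on a sampling rule that the protocol leaves open.

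**Against chance error.** Share of 100,000 simulated trials in which the exact 95% interval contains the true sensitivity/specificity, with 28 independent verified lesions (an assumption) and p = 0.5:

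| | r = 2 | r = 4 |
|---|---|---|
| All PET-selected | 90%/87% | 58%/57% |
| Half pre-PET | 96%/95% | 91%/89% |

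With 12 lesions, all PET-selected, the figures are 99.8%/95% at r = 2 and 98%/86% at r = 4.

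**PPV and NPV.** With equal IHC-positive shares in both sources they stay at 78% and 73% whatever r is. That breaks in two ways:
- Keep r = 2, f = 0.5 and p = 0.5 in the PET-selected part, but let the pre-PET tissue be 30% or 70% IHC-positive. PPV/NPV become 71%/81% or 83%/62%.
- Assume PPV 0.90 in hot and 0.656 in warm PET-positive lesions. Sampling hot over warm 2:1 gives (2 × 0.90 + 0.656)/3 = 82%; 4:1 gives (4 × 0.90 + 0.656)/5 = 85%.

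**The case against.** The strongest reply is that partial verification is not shown to occur. Eligibility needs only one lesion that can be biopsied, and where a patient has one lesion the PET cannot steer the choice. At patient level, verification looks close to complete, because screening IHC is collected and patients without recent untreated tissue are to be sampled. This stands as a limit: the concern applies to patients with several lesions, analysed by lesion. Since section 10.4.3 does not name the unit, it cannot be ruled out either.

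A second reply is that pre-PET tissue dilutes the bias. It does, as the table shows. A reader might infer from the 58%/57% cell that the intervals would mislead at the upper end of the planned size. The documents do not support that: it needs a fourfold ratio found nowhere in them and no pre-PET tissue at all, and 28 is a number of subjects. Verified lesions could be more or fewer, and would be clustered within patients.

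Third, the results are exploratory: section 10.2 sets no hypothesis, no accuracy measure is a listed endpoint, and section 10.1 promises a formal SAP before database lock. This bears on weight. It also makes now a cheap time to act, because a PET call cannot be locked retrospectively.

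**Conclusion.** The concern holds in a limited form. Followed as written, the plan yields sensitivity and specificity that partly reflect lesion choice whenever patients have several lesions and the analysis is by lesion. The size and direction are unknown, and every percentage above rests on assumed accuracy, IHC-positive share and sampling ratio. With half of the tissue pre-PET and 28 independent lesions, chance error usually dominates.

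Two stronger readings should be resisted. One is that sensitivity will be overstated: that follows from hottest-lesion sampling alone, whereas the protocol also names sampling of both kinds as its ideal. The other is that PPV and NPV are a safe alternative: they move with preference for the hottest lesion and, when sources are combined, with differing IHC-positive shares.

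The rule giving post-dose tissue precedence is not at fault. Pathology may be up to a year old under the inclusion criteria, and Table 3 itself notes that prior treatment alters measured expression. The effect is on interpretation of an exploratory result, not on an error rate. It merits consideration rather than being critical.

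**What to change.** In section 10.4.3, or in the SAP promised in section 10.1:

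1. Make the lesion the unit of analysis and acknowledge clustering within patients. Tabulate verified lesions by PET result and tissue source (taken before the study PET, or selected on it). Report sensitivity, specificity, PPV and NPV separately by source, state that the PET-selected figures apply to the sampled lesions only, and do not describe PPV and NPV as free of selection effects.
2. Have the IRC record and lock each lesion's PET call before it sees that lesion's IHC, screening IHC included. Release the IHC after the lock, so that any dose-escalation review that uses it can proceed.
3. Reconcile sections 7.3.3 and 10.4.3 with Table 4, footnote 12, on where post-dose IHC is performed.

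Keep the post-dose truth rule. A formal verification-bias correction is not recommended.

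The cost is wording, two recorded items per verified lesion (PET result and tissue source) and a lock date. No extra biopsies, scans or readers are needed. The drawback is small subgroups with wide intervals: 5 of 7 in one source has an exact 95% interval of 29% to 96%.

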10.4.4 Safety Analyses

Safety evaluation indicators

- AE/SAE/SUSARs.
- Vital signs: Blood pressure, pulse, respiration, and body temperature.
- Physical Examination: Assessment of changes in physical examination of subjects before and after drug administration.
- Laboratory tests: Blood routine, blood biochemistry, urine routine, and coagulation function.
- Electrocardiogram: Evaluate changes in subjects' electrocardiogram before and after administration.
- Examination of injection site: Evaluate the condition of the injection site after administration, such as redness, swelling, heat, pain, itching, etc.
- Systemic and organ radiation distribution: Regions of interest (ROI) such as the brain, liver, and heart are delineated based on the iteratively reconstructed PET/CT imaging results to obtain the mean and maximum tumor volume radioactivity at different time points. The radioactive decay of each source organ and the radiation dose of all target organs are calculated.
- Radiation exposure in ambient environment: Radiation exposure in ambient environment measured by a radiation detector.
- Researcher exposure: such as recording exposure through personal radiation dosimeters worn by researchers.

10.4.5 Baseline Descriptive Statistics

Descriptive statistics for demographics and other baseline features is conducted.

For continuous variables, the number of cases, mean, standard deviation, median, quartile, minimum, and maximum are calculated.

For enumeration and ranked data, counts and frequencies are calculated.

10.4.6 Planned Interim Analyses

Not applicable.

10.4.7 Exploratory Analyses

Not applicable.

10.5 Determination of Sample Size

This is an exploratory study and sample size determination is not based on any hypothesis testing. SNA002 is a ⁶⁸Ga-labeled radiodiagnostic reagent that has no pharmacological or toxicological effects during clinical use. Based on the sample size for ⁶⁸Ga-NOTA-2Rs15d (a total of 20 subjects, with 5–7 subjects per group) and ⁸⁹Zr-Df-IAB22M2C (a total of 6 subjects, with 1 subject per group), 12–28 subjects are intended to be enrolled in this trial. Each group is planned to include 3 to 7 subjects, and the number of subjects will be adjusted based on the imaging results. The detailed rules for adjustment are shown in the “General considerations for dose escalation” section. A total of 12–28 subjects will be enrolled into the effective dose group to allow sufficient observation of preliminary safety and common adverse reactions.

11 Source Documents and Access To Source Data/Documents

Source documents are defined as original documents recording observation results and clinical study activities. Source documents include but are not confined to the following: progress notes, electronic data, screening log, and data recorded by automated instruments. For more details, please refer to the source document list. The investigators should maintain all source documents related to the clinical trial. These source documents will be submitted to the authorized staff (see below) for direct review as per ICF:

- Clinical trial team and authorized staff
- Sponsor and its authorized agent
- Ethics committee
- The supervisory bodies and other staff from governmental agencies who are responsible for safeguarding the safety of the subjects

Direct review consists of the inspection, analysis, verification and reproduction of records and reports which are of great significance for evaluating the clinical trial by the supervisory bodies.

The source document list can be found in the source document list table.

12 Quality Assurance and Quality Control

- Quality control measures of the laboratory : The laboratory should provide documents such as quality control certificate.
- Investigators participating in the clinical trial must have the professional skills, qualifications, and competence related to clinical trials. They must pass the qualification examinations. Minimum mobility of the investigators is required during the clinical trial.

- Before the clinical trial, the staff participating in the clinical trial should receive training on the protocol, current GCP, and SOP related to the present clinical trial.
- The study site should designate 1-2 imaging instruments for use in the clinical trial. The selected instruments must have a good performance and can completely satisfy the requirements of the trial. The designated instruments should be attached with relevant certification documents.
- The operating staff of the instruments should be authorized by PI and the authorization remains valid during the clinical trial. Moreover, they should be familiar with the protocol and the standard operating procedure of the imaging instruments.
- The specific procedure and parameters of imaging can be found in the standard operating procedure.
- The drug preparation staff should have the qualifications for radioactive drug preparation. They should be authorized by PI, and the authorization remains valid during the clinical trial.

13 Ethics/Protection of Human Subjects

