Number of Patients Planned	The study plans to recruit approximately 12-28 patients. The actual sample size will be dependent upon meeting the dose escalation criteria.
Objectives	
Primary objectives
 
To evaluate the safety and tolerability of single doses of SNA002 administered intravenously in patients with solid tumors
 
To assess the biodistribution of SNA002 in patients with solid tumors
 
Secondary objectives
 
To assess the radiation dosimetry of SNA002 in patients with solid tumors
 
To assess the radiation dose of SNA002 in the blood of patients with solid tumors
 
To assess the PET imaging characteristics of SNA002 in patients with solid tumor
 
To identify the optimal dose
 
To identify optimal image timing window
 
Exploratory objectives
 
To explore the correlation between the PET imaging characteristics of SNA002 and PD-L1 binding and the histological PD-L1 expression patterns.
 
To explore the positive and negative predictive efficacy of [⁶⁸Ga] Ga-NOTA-SNA002.

Endpoint	
Primary Endpoints
 
Incidence of treatment-emergent adverse events (TEAEs) and serious adverse events (SAEs)
 
Dosimetry and biodistribution
 
Secondary Endpoints
 
Radiation dosimetry of SNA002
 
Radiation exposure: detecting radioactivity in the blood
 
Recommended diagnostic dose of SNA002
 
Optimal imaging window
 
SUV_{max} (Standardized uptake value), SUV_{mean}, tumor to background ratio, and tumor to blood ratio.
 
PK parameters of SNA002: Including but not limited to maximum serum concentration (C_{max}), time to reach maximum serum concentration (T_{max}), and area under the serum concentration versus time curve from time zero to time (AUC_{0-τ}), and terminal half-life (T_{1/2}).
 
Immunogenicity: incidence of anti-drug antibodies

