6.1.7.2 Dose Escalation Schedule

The dose escalation is determined through both imaging results and safety results:

Imaging:

The Imaging Reviewer Committee consisted of the principal investigator and nuclear medicine physicians.

- 1) If the first three positive tumor lesions in a certain dose group judged by the IRC having a high image quality (such as $\text{T}/\text{B} > 1.5$, etc.), it can be decided from the imaging perspective to increase to the next dose group after continuing to enroll 3-4 cases in this dose group, or directly increase to the next dose group for further exploration;
→If the quality of the first 3 cases in the subsequent dose group is comparable to that in the previous dose group, the IRC shall discuss whether to discontinue further enrollment from a

imaging perspective (e.g. The image quality of the first 3 cases in the 0.3mg dose group is similar to that in the 0.1mg dose group, then stop recruiting, and the 0.1mg dose was identified as the optimal image dose).

- If the quality of the first 3 cases in the posterior dose group is higher than prior, another 3 to 4 cases will be enrolled. After the completion of the posterior dose group, the IRC will discuss and decide whether this group should not be explored from the imaging aspect (e.g. The image quality of the first 3 cases in the 0.3mg dose group is higher than that in the 0.1mg dose group, then 3-4 cases , and the subsequent dose exploration was not carried out, and the 0.3mg dose was identified as the optimal image dose).

- 2) If the first three positive tumor lesions in a certain dose group judged by IRC present poor imaging quality (such as $T/B \leq 1$) or nonvisualization (functional imaging without nuclides), the decision of stopping enroll in this dose group can be made from an imaging perspective, and the dose group can directly increase to the next or second dose group (for example, if the imaging quality of the 0.1mg dose group is poor in three consecutive cases, the dose group can increase to the 0.3mg or 0.5mg dose group);
- 3) If the last dose group shows nonvisualization of the positive tumor lesions determined by the IRC in the first three cases, discussion will be conducted to determine whether to adjust the subsequent dose from the imaging perspective or terminate the entire clinical trial.

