- 4) After the dose escalation of all dose groups is completed, the imaging expert committee and the principal investigator will decide whether to continue enrolling 3-4 subjects in a certain initially identified optimal dose group for further exploration.

Security:

The principal investigator determines whether to increase the dose from the perspective of safety. Dose escalation should be stopped if one of the principles happen:① at least half of subjects in a dose group experience CTCAE grade 2 (or moderate) or above adverse reactions;② or at least 1/3 subjects experience CTCAE grade 3 (or severe) or above adverse reactions;③ or one serious adverse reaction in certain group.

The dose escalation will be determined by the principal investigator based on both imaging and safety results. During the clinical trial, based on the principle of subject protection, the dose group can be rapidly escalated to the subsequent dose group if nonvisualization or the above safety events happens after only one subject enrolled according to the investigator's discretion.

[figure not shown]

Figure 3 Dose escalation

After the dose escalation of all dose groups is completed, the imaging expert committee and the principal investigator will decide whether to enroll another 3 or 4 patients in the identified optimal dose group.

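### Section 10.5 assigns the trial-wide total of 12–28 subjects to a single dose group, which the plan sizes at 3–7

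*Combined protocol and SAP*

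**What the plan says.** Section 10.5 uses the range 12–28 twice, for two different things.

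- **Trial total.** After citing two precedent tracers, it says that 12–28 "subjects are intended to be enrolled in this trial". It adds: "Each group is planned to include 3 to 7 subjects, and the number of subjects will be adjusted based on the imaging results".
- **One dose.** Its last sentence says that a total of 12–28 "subjects will be enrolled into the effective dose group to allow sufficient observation of preliminary safety and common adverse reactions".

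The Protocol Summary supports the first use. Under Number of Patients Planned it says "The study plans to recruit approximately 12-28 patients", and it discloses that this may vary: "The actual sample size will be dependent upon meeting the dose escalation criteria". Its Study Design entry lists four dose levels (0.1, 0.3, 0.5 and 0.9 mg) with 3–7 patients at each.

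Section 6.1.7.2 sets how a dose group fills. The first three subjects are assessed. If image quality is high, escalation may follow "after continuing to enroll 3-4 cases in this dose group", or may follow directly. If quality in a later group "is higher than prior, another 3 to 4 cases will be enrolled". Once escalation is complete, the imaging committee and the principal investigator "will decide whether to enroll another 3 or 4 patients in the identified optimal dose group".

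**The concern.** The same range cannot be both the size of the whole trial and the size of one of its four groups. The last sentence of 10.5 is also the only one there that links the number of subjects to what will be learned about safety. Safety and tolerability is a primary objective, and the recommended diagnostic dose is a secondary endpoint. An ethics committee or regulator reading the sentence literally would expect 12–28 exposures at the dose taken forward, and would judge the safety information at that dose accordingly. The escalation rules do not deliver that number at any one dose.

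**Working it through.** **Step 1: reproduce the plan's figure.** Inputs: four dose levels (Protocol Summary, Study Design) and 3–7 subjects per group (Protocol Summary and 10.5).

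- Lower end: 4 × 3 = 12.
- Upper end: 4 × 7 = 28.

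The range is therefore exactly the total over four groups. Section 6.1.5 speaks of 3–4 dose groups. With three groups the total would be 3 × 3 = 9 to 3 × 7 = 21, which does not make 12–28 a single-group size either.

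**Step 2: how many subjects one dose can hold under 6.1.7.2.**

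- First three only: 3.
- With the 3–4 further cases: 3 + 3 = 6 or 3 + 4 = 7.
- With the optional 3–4 after escalation, added to a group left at three: again 6 or 7.
- With the optional 3–4 added to a group already at 6 or 7: 9, 10 or 11 (maximum 7 + 4 = 11).

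The documents do not say whether the option may take a group beyond the planned 3–7. If it may not, the maximum is 7. If it may, the maximum is 11. Both are below 12.

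**Step 3: what the difference means for safety information.** The plan gives no reaction rate, so the rates here are assumptions. The chance of at least one case among n subjects at true rate p is 1 − (1 − p)^n. The one-sided 95% upper bound on the rate after zero cases is 1 − 0.05^(1/n).

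| n at the dose | p = 5% | p = 10% | p = 20% | Upper bound after zero cases |
|---|---|---|---|---|
| 3 | 14% | 27% | 49% | 63% |
| 7 | 30% | 52% | 79% | 35% |
| 11 (only if the option may exceed 7) | 43% | 69% | 91% | 24% |
| 12 (literal reading, low end) | 46% | 72% | 93% | 22% |
| 28 (literal reading, high end) | 76% | 95% | 99.8% | 10% |

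For example, at p = 10% and n = 7, 1 − 0.9^7 = 0.522; at n = 12, 1 − 0.9^12 = 0.718.

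**Step 4: does anything depend on the sentence?** Section 10.2 sets no hypothesis test and 10.4.6 has no interim analysis. The escalation stops in 6.1.7.2 use fractions of a group or one serious reaction. The termination rule in 5.4 and the halting rule in 8.5 use a fraction or a count of events. None of them uses 12–28.

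**The case against.** The strongest reply is that this is a lost plural. The sentence opens by calling 12–28 a total, repeats a range that the same paragraph has just tied to the trial, and sits in a text with many translation slips. Anyone planning enrolment has the Protocol Summary, the per-level table and the rest of 10.5 to go by. This is probably right, and it is why the point is minor. It does not make the sentence correct: it belongs to the formal sample-size statement and carries the safety claim.

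A second reply is that the effective dose group means all effective doses together. The wording is singular. Even when pooled, 12–28 would need all four levels to count as effective, while 6.1.7.2 provides for levels that image poorly, stop at three subjects or are skipped.

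A third reply is that 6.1.7.2 mentions the post-escalation option twice. Both statements describe the same decision, and the Protocol Summary states it once. Counted twice it would give 7 + 4 + 4 = 15, still far from 28.

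It is also fair to say that the size of the gap depends on the comparison. At 11 against 12 it is small (69% against 72% at a 10% rate). The wide gap to 28 uses the top of a reading that was probably not meant.

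Three stronger inferences are tempting, and the documents do not support them:

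- **That the sample-size arithmetic is wrong.** It is not; 12–28 reproduces exactly as the trial total.
- **That the trial will hold 11 at one dose and up to 32 overall** (7 + 7 + 7 + 11). Both figures assume that the option may exceed 7 per group, which is not stated. Nor is 32 a firm ceiling, because 6.1.8 lets the imaging committee consider a level above 0.9 mg.
- **That a total below 12 is an undisclosed possibility.** Stopping after three subjects at each of two levels would give 6, but both 10.5 and the Protocol Summary say that the number depends on escalation.

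**Conclusion.** The last sentence of 10.5 is inconsistent with the rest of that section, with the Protocol Summary and with 6.1.7.2. The range 12–28 is the planned total over four dose levels. One dose is planned at 3–7 subjects, and at most 11 if the optional 3–4 may be added to a full group. In neither case does one dose reach 12.

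Severity is minor. No design feature or decision rule uses the sentence, and the precedent-based rationale for the total is unaffected. What is affected is the stated strength of the safety information at the selected dose: with 7 subjects and no reactions, a true rate of up to 35% remains compatible with the data, against 22% for 12 and 10% for 28.

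The conclusion about group size rests on the written rules. Figure 3 is not shown in the available text, and I have taken 6.1.7.2 to be the escalation section that 10.5 refers to under a different title. The detection probabilities rest on assumed reaction rates.

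**What to change.** Replace the last sentence of 10.5 with:

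> A total of about 12–28 subjects is planned across the dose groups (3–7 per group) to allow preliminary observation of safety and common adverse reactions in the pooled safety set; the selected dose itself is planned to hold 3–7 subjects, plus any optional 3–4 added under 6.1.7.2.

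Do not write 11 or 32 into 10.5 unless the sponsor confirms that the option may take a group beyond 7. If it does, the total and the per-level table in the Protocol Summary must change to match; otherwise the edit would create a new inconsistency.

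The cost is one sentence. Enrolment, the escalation rules and the imaging committee's discretion stay as they are. The sponsor gives up only a more favourable statement about safety information than the design supports.
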